17. FINANCING AND INSURANCE

Financing and insurance information is provided as a separate agreement.

18. PUBLICATION POLICY

Publication rights and procedures will be outlined in a separate clinical study agreement.

APPENDIX A. Oxygenation Equivalence for Eligibility

Sites located in high-altitude areas (>1500 m above sea level) should use [Table 9](#) to get the appropriate high-altitude equivalents for sea-level oxygenation measurements.

Table 9: High Altitude Equivalents for Sea-Level Oxygenation Measurements

Eligibility Criterion	Protocol-Defined Threshold (Sea-Level Measurement)	High-Altitude Equivalent For Eligibility
Inclusion criterion 5b	O ₂ saturation >93%	O ₂ saturation >90%
Inclusion criterion 5c	SpO ₂ ≤96%	SpO ₂ ≤93%
Exclusion criterion 1 (Phase 1 only)	O ₂ saturation >94%	O ₂ saturation >91%

Signature Page for VV-RIM-00163777 v1.0

ESig Approval

ESig Approval

ESig Approval

ESig Approval

Signature Page for VV-RIM-00163777 v1.0 Approved

10.3.	Criteria for Potentially Clinically Significant Values (PCSV)	59

LIST OF TABLES

Table 1:	Cohorts of Hospitalized Patients in Study R10933-10987-COV-2066	15
Table 2:	Statistical hypotheses.....	16
Table 3:	Primary Clinical Efficacy Endpoints and Populations	29
Table 4:	Secondary Virologic Efficacy Endpoints and Populations.....	30
Table 5:	Secondary Clinical Efficacy Endpoints and Populations	31
Table 6:	Secondary Clinical Endpoints based on Proportions of Patients with Outcome.....	31
Table 7:	Cumulative Incidence of Event Endpoints - Definitions of Events and Censoring Rules.....	32

Table 8:	NCI-CTCAE Severity Grading System for Adverse Events.....	34
Table 9:	Hierarchical testing order	41
Table 10:	Time Window for Summary of Swab Samples for SARS-CoV-RT-qPCR	48
Table 11:	Time Window for Summary of Laboratory Variables and Biomarkers	48

LIST OF FIGURES

Figure 1:	Phase 1 – Study Flow Diagram	19
Figure 2:	Phase 2 – Study Flow Diagram	20

List of Abbreviations and Definition of Terms

Abbreviation	Definition
ADA	Anti-drug antibody
AE	Adverse event
AESI	Adverse event of special interest
ALT	Alanine aminotransferase
ANCOVA	Analysis of covariance
aPTT	Activated partial thromboplastin time
AST	Aspartate aminotransferase
ATC	Anatomical Therapeutic Chemical
BMI	Body Mass Index
COVID-19	Coronavirus Disease 2019
CPK	Creatine phosphokinase
CRF	Case report form (electronic or paper)
CRP	C-reactive protein
CSR	Clinical study report
ECG	Electrocardiogram
ECMO	Extracorporeal membrane oxygenation
EUA	Emergency Use Authorization
FAS	Full Analysis Set
FDA	United States Food and Drug Administration
FiO ₂	Fraction inspired oxygen
ICH	International Council for Harmonisation
ICU	Intensive care unit
IDMC	Independent Data Monitoring Committee
IWRS	Interactive Web Response System
IV	Intravenous
IVIG	Intravenous immunoglobulin
mFAS	Modified Full Analysis Set
MedDRA	Medical Dictionary for Regulatory Activities

Abbreviation	Definition
NCA	Non-compartmental analyses of Pharmacokinetic parameters
NCI-CTCAE	National Cancer Institute-Common Terminology Criteria for Adverse Events
NLR	Neutrophil-lymphocyte ratio
NP	Nasopharyngeal
PCSV	Potentially Clinically Significant Value
PD	Pharmacodynamic(s)
PK	Pharmacokinetic(s)
PT	Preferred Term
RBC	Red Blood Cell
RNA	Ribonucleic Acid
Regeneron	Regeneron Pharmaceuticals, Inc.
REGN-COV2 (R10933+R10987)	Co-administered REGN10933 and REGN10987 combination therapy
SAE	Serious adverse event
SAF	Safety analysis set
SAP	Statistical analysis plan
SARS-CoV-2	Severe acute respiratory syndrome coronavirus 2
SAS	Statistical Analysis System
SOC	System organ class
SpO ₂	Peripheral capillary oxygen saturation
TEAE	Treatment-emergent adverse event
ULN	Upper Limit Normal
US	United States (of America)
WBC	White blood cell
WHO	World Health Organization
WHODD	World Health Organization Drug Dictionary

1. OVERVIEW

1.1. Background/Rationale

R10933-10987-COV-2066 (referred to as study “COV-2066” hereafter) is an adaptive phase 1/2/3, randomized, double-blinded, placebo-controlled master protocol to evaluate the efficacy and safety of co-administered REGN10933+REGN10987 combination therapy (“REGN10933+REGN10987”) in hospitalized adult patients with COVID-19.

The purpose of this statistical analysis plan (SAP) is to ensure the integrity of the study results by pre-specifying the statistical approaches for the analysis of study data prior to the final database lock. This final version of the SAP is intended to be a comprehensive and detailed description of the strategy and statistical methods to be used in the analysis of final data from all phases (phase 1, phase 2, and phase 3) and all cohorts (cohort 1A, cohort 1, cohort 2, and cohort 3), based on Protocol Amendment 7 (dated 07 July 2021).

Summary of Study Conduct and Patient Enrollment

In this study, patients were enrolled in one of the following 4 cohorts based on disease severity at randomization:

- **Cohort 1A (Room Air):** Patients with COVID-19 symptoms but not requiring supplemental oxygen
- **Cohort 1 (Low Flow Oxygen):** Patients with O₂ saturation >93% on low-flow oxygen via nasal cannula, simple face mask, or other similar device
- **Cohort 2 (High-Intensity Oxygen):** Patients on high-intensity oxygen therapy* but not on mechanical ventilation

**High-intensity oxygen therapy is defined as the use of non-rebreather mask with an oxygen flow rate of at least 10 L/min; use of a high flow device with at least 50% FiO₂, or use of non-invasive ventilation to treat hypoxemia*

- **Cohort 3 (Mechanical Ventilation):** Patients on mechanical ventilation

In the first-in-human (FIH) phase 1 portion of the study, patients were enrolled into cohort 1 only. Subsequently, in phase 2, patients were enrolled into all 4 cohorts.

On 30 October 2020, an Independent Data Monitoring Committee (IDMC) recommended pausing enrollment into cohort 2 and cohort 3 based on a potential safety imbalance, while proceeding with enrollment in cohort 1A and cohort 1. All cohort 2 and 3 patients enrolled at the time of the recommendation continued in the study and were followed up through the end of study visit as per the protocol. This IDMC recommendation on enrollment was maintained for the duration of the study.

An unblinded phase 1/2 analysis was performed on the patients who were randomized through 01 December 2020 in phase 1 (cohort 1 only) and phase 2 (cohorts 1, 2, and 3) using a data cutoff date of 09 December 2020, based on a database lock on 22 December 2020 (refer to the phase 1/2 SAP dated 21 December 2020 for details). Phase 2 cohort 1A was not included in the analysis. All patients enrolled into cohort 1 after 01 December 2020 were considered to be part of phase 3.

On 09 April 2021, the Sponsor made a business decision to terminate patient enrollment in this study due to extremely low recruitment over several months. This decision was not based on any safety concerns. Accordingly, phase 3 cohort 1 and phase 2 cohort 1A enrollment was prematurely terminated. Until this time, only cohort 1 patients were enrolled into the phase 3 portion of the study. All ongoing subjects were followed up through their end of study visit as per the protocol.

Cohort 1 reached its phase 2 enrollment goal first, and phase 3 cohort 1 started enrollment after 01 December 2020. As cohort 1A never reached its predetermined phase 2 enrollment goal of 1000 patients, phase 2 cohort 1A and cohort 1 enrolled concurrently. Phase 2 cohort 1A data were handled and overseen similar to phase 3 cohort 1 data.

Given much smaller sample size than anticipated as a result of early termination of enrollment, the Sponsor has elected to pool phase 2 cohort 1A and phase 3 cohort 1 and combine the REGN10933+REGN10987 2.4g and 8.0g dose groups for the primary analyses.

Overall, approximately 2252 subjects were randomized in study COV-2066:

Phase 1

- Cohort 1: 60 patients

Phase 2

- Cohort 1A: 609 patients
- Cohort 1: 629 patients
- Cohort 2: 164 patients
- Cohort 3: 35 patients

Prematurely Terminated phase 3

- Cohort 1 (ie, subjects randomized after 01 Decemeber 2020 in cohort 1): 755 patients

This final SAP outlines the strategy and statistical methods to be used in the final analysis of data from all phases and all cohorts in the prematurely terminated study COV-2066, as below:

Efficacy Analysis

The efficacy analysis will be performed for the modified full analysis set (mFAS, defined in Section 3.1) of the following pooled cohort of patients and individual subsidiary cohorts, representing the totality of patients in this prematurely terminated study who were not unblinded in the database lock on 22 December 2020. In this document, the prematurely terminated phase 3 cohort 1 is referred as phase 3 cohort 1 and prematurely terminated phase 2 cohort 1A as phase 2 cohort 1A.

- Pooled phase 3 cohort 1 and phase 2 cohort 1A
- Phase 3 cohort 1
- Phase 2 cohort 1A

In each of these data sets (ie, the 2 terminated cohorts and the pooled cohort), the analyses will be conducted in the mFAS for the following patient populations. The mFAS is defined as patients that have a positive central-lab confirmed SARS-CoV-2 RT-qPCR result from an NP

swab sample and the efficacy analysis was conducted in the mFAS to ensure detectable virus was present at baseline.

- Seronegative mFAS
- High Viral Load mFAS, where high viral load is defined as $>10^6$ copies/mL at baseline
- Overall mFAS

The **primary** virologic endpoint is time-weighted average change from baseline viral load in nasopharyngeal (NP) samples through Day 7. The primary analysis will be performed in the Seronegative mFAS population that is combined across the 2.4 g and 8g doses and pooled across phase 3 cohort 1 and phase 2 cohort 1A.

The **primary** clinical endpoint is death or mechanical ventilation. It will be estimated based on the proportion of patients who died or went on mechanical ventilation from Day 6 through Day 29, where events occurring during the first 5 days will excluded because of the notion that clinical impact would occur only after achieving several days of viral suppression. This observation was noted in the analysis of data from phase 1/2 portion of this study. In addition, the endpoint of death or mechanical ventilation from Day 1 through Day 29 will also be evaluated. The primary analysis will be performed for the High Viral Load mFAS, Seronegative mFAS, and the Overall mFAS in the pooled phase 3 cohort 1 and phase 2 cohort 1A and combined across the 2.4 g and 8 g doses of REGN10933+REGN10987. To control alpha at a strict 0.05 level, the two primary endpoints will be tested hierarchically, with the virologic endpoint tested first.

Safety Analysis

The safety analysis will be performed for the following cohorts, separately. Patients in phase 1/2 cohort 1, phase 2 cohort 2 and cohort 3 are included into the analysis because more safety data were collected for the patients after the database lock on 22 December 2020.

- Phase 2 cohort 1A
- Phase 2 cohort 2
- Phase 2 cohort 3
- Phase 1/2/3 cohort 1 combined

Pharmacokinetics (PK) and Immunogenicity Analysis

The PK and ADA analysis will be performed for phase 1/2/3 cohort 1 combined, phase 2 cohort 1A, phase 2 cohort 2, and phase 2 cohort 3, separately. The NAb analysis will be performed for phase 2/3 patients.

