3.3.2. Summary of Risks

Important Identified Risks. As with other protein therapeutics, hypersensitivity reactions, including acute infusion-related reactions (IV administration) or injection site reactions (SC administration), may develop immediately or within a few hours to days after study drug administration. Hypersensitivity reactions, including anaphylaxis, infusion-related reactions or injection site reactions, have been observed in patients who received REGN10933+REGN10987 during ongoing clinical trials.

Important Potential Risks. The important potential risks of REGN10933+REGN10987 are the clinical consequences of immunogenicity and embryo-fetal toxicity.

Protein therapeutics carry the potential risk of an immunogenic response in the form of anti-drug antibody (ADA) and NAb development following administration, with possible consequences on safety and efficacy. Therefore, blood samples for immunogenicity assessment will be collected during the studies.

Reproductive and developmental toxicology studies have not been conducted; therefore, the effects of REGN10933, REGN10987, and REGN10933+REGN10987 combination therapy on the fetus and reproductive organs in males and females are unknown. Human immunoglobulin G1 (IgG1) antibodies are known to cross the placental barrier and are present in breast milk; therefore, the REGN10933+REGN10987 combination therapy have the potential to be transferred from the mother to the developing fetus or a breastfed child. Given the high affinity and specificity of REGN10933 and REGN10987, off-target pharmacological effects are not anticipated in either the mother or the fetus, and no off-target binding of REGN10933 or REGN10987 was observed in any of the human or monkey tissues evaluated ex vivo in tissue cross-reactivity studies. However, it is unknown whether the potential transfer of the combination of REGN10933+REGN10987 therapy provides any treatment benefit or risk to the developing fetus or a breastfed child.

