6.1.2. Study Duration

Phase 1 (Cohort 1 only)

The phase 1 portion of the study will last up to 170 days. See [Table 1](#) for the schedule of events and sample collections:

- **Screening/Baseline:** Patients will undergo a screening and baseline period for up to 2 days (day -1 to 1).
- **Hospitalization and post-discharge period:** Patients will be assessed daily up to day 29 while hospitalized. Patients who are discharged before day 29 will be followed up—in person for sample collections, and may also be followed up by phone or telemedicine for assessments. After day 29, all patients will be followed up monthly.
- **End of study (EOS):** On day 169, patients will have an in-person EOS visit for sample collection and assessments.

Figure 2: Study Flow Diagram, Phase 1

Phase 2 (Cohort 1A, Cohort 1, Cohort 2*, and Cohort 3*) and Phase 3 (Cohort 1)

* Per IDMC recommendation first received on 30 October 2020, and reiterated through 19 February 2021, patient enrollment in cohort 2 and cohort 3 has been placed on hold.

[figure not shown]
The phase 2 and phase 3 portions of the study will last up to 58 days. See [Table 2](#) for a schedule of events and sample collections.

Patients in phase 2 (cohort 1A) and phase 3 (cohort 1) who consent to the **long COVID sub-study** at participating sites will follow the main study Schedule of Events ([Table 2](#)) until day 57, then

follow the long COVID sub-study Schedule of Events (Table 3) from day 58 to day 180. Patients who do not consent to these additional assessments will follow Table 2 until day 57.

- **Screening/Baseline:** Patients will undergo a screening and baseline period for up to 2 days (day -1 to 1).
- **Hospitalization and post-discharge period:** Patients will be assessed daily up to day 29 while hospitalized. Patients who are discharged before day 29 will be followed up in person for sample collections, and may also be followed up by phone or telemedicine for assessments. After day 29, all patients will be followed up weekly.
- **End of study (for patients not participating in the long COVID sub-study at participating sites):** On day 57, patients will be followed up by phone or telemedicine for an EOS visit.
- **Long COVID sub-study follow-up (at participating sites):** On day 120, patients will be followed up for questionnaires and sample collections.

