Details for sample size calculations are provided in the protocol.

Finalization of the sample size and patient population for phase 3 was planned to be subject to change and would be determined after review of phase 2 data. However, enrollment of patients into the study was terminated prematurely by the Sponsor on 09APR2021 because of extremely slow enrollment in the months preceding the decision. The sample size of phase 3 was not re-estimated.

Approximately 2252 patients were randomized in the study, which includes 60 patients in phase 1 Cohort 1, 629 in phase 2 Cohort 1, 755 in planned phase 3 Cohort 1, 609 in phase 2 Cohort 1A, 164 in phase 2 Cohort 2 and 35 in phase 2 Cohort 3.

[figure not shown]
Assuming the proportion of patients who died or went on mechanical ventilation from day 1 to day 29 in placebo group is 13.1% which is same as the blinded proportion in the Seronegative mFAS patients of the pooled phase 3 cohort 1 and phase 2 cohort 1A and alpha is 0.05 2-sided, the minimal significant difference in relative risk reduction between the REGN10933+REGN10987 2.4g and 8.0g combined dose group and placebo group is 29.0%, 41.2%, and 36.6% for overall mFAS, Seronegative mFAS, and High Viral Load mFAS patients, respectively.

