5.9. Analysis of Immunogenicity Data

5.9.1. Analysis of ADA Data

Immunogenicity variables will be summarized using descriptive statistics.

Immunogenicity will be characterized by the ADA responses and titers observed in subjects in the ADA analysis set. ADA response categories and titer categories are defined as follows:

ADA response categories:

- ADA Negative, defined as ADA negative response in the ADA assay at all time points, regardless of any missing samples.
- Pre-existing immunoreactivity, defined as either an ADA positive response in the ADA assay at baseline with all post first dose ADA results negative, OR a positive response

at baseline with all post first dose ADA responses less than 9-fold over baseline titer levels.

- Treatment-emergent response, defined as an ADA positive response in the ADA assay post first dose when baseline results are negative or missing. The treatment-emergent responses will be further characterized as Persistent, Indeterminate or Transient.
 - Persistent Response (only applicable to phase 1) – Treatment-emergent ADA positive response with two or more consecutive ADA positive sampling time points, separated by at least 16-week period (based on nominal sampling time), with no ADA negative samples in between, regardless of any missing samples.
 - Indeterminate Response –Treatment-emergent ADA positive response with only the last collected sample positive in the ADA assay, regardless of any missing samples.
 - Transient Response –Treatment-emergent ADA positive response that is not considered persistent or indeterminate, regardless of any missing samples.
- Treatment-boosted response, defined as a positive response in the ADA assay post first dose that is greater than or equal to 9-fold over baseline titer levels, when baseline results are positive.

Titer categories (Maximum titer values)

- Low (titer <1,000)
- Moderate (1,000 ≤ titer ≤ 10,000)
- High (titer >10,000)

The following analysis will be provided:

- Number (n) and percent (%) of ADA-negative subjects (pre-existing immunoreactivity or negative in the ADA assays at all time points) by treatment arms
- Number (n) and percent (%) of treatment-emergent ADA positive subjects by treatment arms and ADA titer categories
 - Number (n) and percent (%) of persistent treatment-emergent ADA positive subjects
 - Number (n) and percent (%) of indeterminate treatment-emergent ADA positive subjects

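### The final SAP's only cohort 1 ADA grouping pools phase 1 (sampled to day 169) with phase 2/3 (apparently sampled to about day 29), with no common time window

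*SAP*

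**What the plan says.** SAP section 1.1 gives the grouping: "The PK and ADA analysis will be performed for phase 1/2/3 cohort 1 combined, phase 2 cohort 1A, phase 2 cohort 2, and phase 2", with cohorts 1A, 2 and 3 each reported alone. Protocol section 11 has the same rule.

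SAP section 5.9.1 calls a response treatment-emergent if any post-dose ADA result is positive and the baseline is negative or missing. No time limit is set. The planned output is "Number (n) and percent (%) of treatment-emergent ADA positive subjects by treatment arms and ADA titer categories", that is, split by arm and titer but not by phase. Persistent response is restricted to phase 1, and its denominator is not stated.

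Follow-up differs by phase in protocol section 6.1.2:
- Phase 1: "On day 169, patients will have an in-person EOS visit for sample collection and assessments".
- Phases 2 and 3, outside the long COVID sub-study: "On day 57, patients will be followed up by phone or telemedicine for an EOS visit".

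Protocol section 3.3.2 explains why immunogenicity is measured: "The important potential risks of REGN10933+REGN10987 are the clinical consequences of immunogenicity and embryo-fetal toxicity".

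**The concern.** The chance of at least one positive sample rises with the length of sampling. A percentage that combines patients sampled for about four weeks with patients sampled for about 24 weeks is not an incidence over any definable period. It is close to a day-29 figure, with a small number of longer-followed patients added.

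The SAP itself shows that the phases are not comparable. Persistent response needs positives at least 16 weeks (112 days) apart, while phases 2 and 3 last at most 58 days, so the category is limited to phase 1. Indeterminate response (only the last collected sample positive) and transient response (the remainder) also depend on when sampling stops, yet they are tabulated across all three phases.

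At stake is whether the report shows the long-term ADA data in a readable form. Phase 1 holds the only evident ADA sampling beyond about day 29. NAb analysis is confined to phases 2 and 3, so ADA status and titer are the late immunogenicity measures available.

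**Working it through.** **Inputs**
- Cohort 1 counts (SAP 2.3): "60 patients in phase 1 Cohort 1, 629 in phase 2 Cohort 1, 755 in planned phase 3 Cohort 1".
- Other randomized counts (SAP 1.1): 609 in cohort 1A, 164 in cohort 2, 35 in cohort 3.
- Allocation 1:1:1 in every phase (SAP 2.1).
- ADA analysis set (SAP 3.4): treated patients with at least one post-dose ADA result. Its size is not given, so randomized counts stand in for it.
- ADA rates: none in the documents. All rates below are assumptions.

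**Check of the counts.** SAP 1.1 states: "Overall, approximately 2252 subjects were randomized in study COV-2066". The parts give 60 + 609 + 629 + 164 + 35 + 755 = 2252, which agrees.

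**Share of phase 1 in the pool.** 60 + 629 + 755 = 1444, and 60/1444 = 4.2%. By arm this is 20 of about 481 (1444/3 = 481.3), the same ratio.

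**Where phase 2/3 ADA sampling ends.** The ADA rows of the schedule tables are too damaged in extraction to read the days. The surrounding text points to about day 29:
- The day 57 end-of-study contact is by phone or telemedicine (protocol 6.1.2).
- SAP 2.4 describes phone calls after day 29 for phase 3.
- Protocol 9.1.3 gives late withdrawals in phase 2 a phone visit, but those in phase 1 a visit with samples.
- The long COVID schedule (protocol Table 3) lists no ADA sample.

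**Dilution of late-only ADA.** Take ADA that first turns positive after phase 2/3 sampling has ended. It can be seen only in phase 1. Let r be the proportion of phase 2/3 patients who are ADA-evaluable, relative to phase 1. The dilution factor is 1 + r × 1384/60, where 1384 = 629 + 755.

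| r (assumed) | Factor |
|---|---|
| 0.5 | 12.5 |
| 0.75 | 18.3 |
| 0.9 | 21.8 |
| 1.0 | 24.1 |

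With r = 1, an assumed late rate of 10% (6 of 60) adds 6/1444 = 0.42 percentage points to the pooled table; 5% (3 of 60) adds 0.21.

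**Effect on the rate as tabulated.** Let E be the early rate (first positive by about day 29, taken as equal in all phases) and L the late rate. Phase 1 alone would show E + L. The pooled table would show E + L × 60/1444, with r = 1.

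| E | L | Phase 1 rate | Pooled rate | Ratio |
|---|---|---|---|---|
| 1% | 5% | 6% | 1.21% | 5.0 |
| 1% | 10% | 11% | 1.42% | 7.8 |
| 5% | 5% | 10% | 5.21% | 1.9 |
| 5% | 10% | 15% | 5.42% | 2.8 |
| 10% | 5% | 15% | 10.21% | 1.5 |
| 10% | 10% | 20% | 10.42% | 1.9 |

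The pooled rate stays within half a percentage point of E in every row. It nearly measures early ADA while carrying no label that says so.

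**The case against.** The analysis is descriptive and affects no hypothesis test. Allocation is 1:1:1 in each phase, so the mixture of follow-up is the same by design in every arm and pooling does not bias comparisons between arms. The grouping also matches the stated phase 1/2/3 cohort 1 immunogenicity objective. All of this stands, and it limits the point to how incidence is reported.

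A reader might go further in four ways that the documents do not support:

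- **That the tabulated ADA rate is 24-fold too low.** That factor applies only to ADA that is late-only, on randomized counts, with equal evaluability. The table reports early plus late ADA.
- **That late ADA would disappear from the report.** SAP 5.9.1 lists all titers for patients with pre-existing, treatment-emergent or treatment-boosted responses, and the persistent row captures some late positives. A listing gives no incidence or denominator, however. Protocol 4.2 also names ADA under phase 1/2 cohort 1 and for phase 3 cohort 1 separately. The phase 1 and phase 1/2 SAPs were not available, so a phase 1 ADA table elsewhere cannot be excluded. SAP 1.2.5 says that this SAP supersedes prior ones, which leaves the status of any such table unclear. The phase 1/2 data cutoff was 09 December 2020; 168 days earlier is 24 June 2020, one day after the phase 1 SAP was approved. Complete day 169 data by that cutoff therefore look unlikely, although dosing dates are not given.
- **That day 29 samples are uninformative because drug is still present.** Protocol 3.2.2 sets a 20 µg/mL serum target for 28 days, but no drug tolerance limit for the ADA assay is given.
- **That phase 2/3 patients are never seen after day 29.** Footnote 10 to protocol Tables 2 and 3 allows weekly follow-up by phone or in person. What is missing is evidence of a scheduled ADA sample.

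Finally, the named risk is the clinical consequences of immunogenicity, not late ADA itself. SAP 5.10.2 allows for exploring ADA status and titer against infusion reactions, hypersensitivity and anaphylaxis.

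**Conclusion.** The point holds as a reporting defect that is cheap to correct. In the final SAP, the only ADA grouping for cohort 1 merges patients with markedly different sampling periods under a definition without a time window. The resulting percentage cannot be read as an incidence to day 29 or to day 169.

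The size depends on what is asked. For ADA first positive after phase 2/3 sampling ends, dilution is about 12- to 24-fold for relative evaluability of 0.5 to 1.0. For the rate actually tabulated, the understatement relative to phase 1 is about 1.5- to 7.8-fold under the assumed rates.

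The day 29 end of phase 2/3 ADA sampling is inferred and should be confirmed against an intact schedule table. If a later sample exists, the common window moves, but phase 2/3 still ends at day 57 in the main study and phase 1 at day 169.

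**What to change.** In SAP 5.9.1:

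- Report treatment-emergent and treatment-boosted ADA (n, %, maximum titer) by arm in separate columns: phase 1 through day 169, and phase 2/3 cohort 1 through its last scheduled ADA sample (about day 29). Use the number sampled as the denominator.
- If a combined cohort 1 figure is kept, restrict it to samples within the common window and label it so.
- State that the denominator for persistent response is phase 1 patients.

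The cost is SAP wording and a split of a planned table. It uses existing data and needs no new visits or samples. The downside is precision, since each phase 1 column has only about 20 patients per arm. That limit already exists in the data, and the pooled table conceals it.
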